6.4.3 Replacement

Subject will be deemed to have commenced the study upon completion of the informed consent process, and any subject who has been discontinued prior to or during the EUS examination will not subsequently be replaced by other subjects.

6.5 Randomization and Blinding

6.5.1 Randomization Implementation

Randomization is conducted according to the study protocol, and the random contents are implemented in an electronic system block-randomized manner ($n = 4$; experimental group/control group = 1). Randomization prior to EUS to decide whether to use EndoAngel. The researchers randomized the random results generated by the electronic system, and the generated random results were stored in the research center. The random time (accurate to minute), random person, subject number and acronym were recorded in the corresponding positions of the electronic system.

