At the same time, the type of pancreatic lesions and the development of the course have abnormal imaging findings of different anatomical structures[18-19]. For example, ultrasound images of pancreatic cancer will show vascular invasion, deformation of the biliopancreatic duct, and metastasis of adjacent organs[20]. The guidelines clearly require that the choice of surgical approach for pancreatic cancer needs to be based on the degree of invasion of the cancer to adjacent important anatomical structures, to maximize the volume sparing of functional pancreatic parenchyma[21]. Complete anatomical scanning can assist in the diagnosis of pancreatic lesions and guide patient treatment and prognosis.

In recent years, artificial intelligence (AI) has been successfully applied in multiple medical fields[22-24]. At present, there have been studies of AI-based endoscopic ultrasonography for the identification of pancreatic lesions[25-27], However, there are no studies of AI-based navigation system for pancreatic endoscopic ultrasonography. Previously, we have successfully developed a standard station scanning navigation system for the pancreas and bile ducts. This system can improve the recognition accuracy of endoscopists for standard stations and enhance the cognitive ability of endoscopic ultrasonography images[28-29].

Based on the previous, we constructed a deep learning-based pancreatic scanning navigation system in EUS, which can assist in identifying important anatomical structures adjacent to the pancreas in real time. and verify its auxiliary performance for endoscopists in clinical practice. In order to improve the quality of EUS and reduce the missed diagnosis of pancreatic lesions.

3. Patient Selection

Male and female subjects aged 18 years or older will require a endoscopic ultrasonography, and voluntarily provide endoscopic ultrasonography imaging data and sign an informed consent form.

Patients not meeting the inclusion criteria or meeting exclusion criteria will not be considered for participation in the study. Patients who met all criteria and signed informed consent may be excluded from the study due to:

- Endoscopists' professional advices/medical reasons (only under very limited conditions to avoid researcher bias).
- Withdraw informed consent.

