3.2. Exclusion criteria

All patients meeting the following criteria will not be considered for participation in the study:

- 1) Has participated in other clinical trials, signed informed consent and was in the follow-up period of other clinical trials.
- 2) Has participated in clinical trials of the drug and is in the elution period of the experimental drug or control drug.
- 3) Drug or alcohol abuse or psychological disorder in the last 5 years.
- 4) Patients in pregnancy or lactation.
- 5) A history of Upper Gastrointestinal surgery.
- 6) Patients with anatomical abnormalities of the upper gastrointestinal tract due to advanced neoplasia
- 7) Patients in whom the presence of clearly defined vital anatomical structures cannot be observed
- 8) Researchers believe that the patient is not suitable to participate in the trial.

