3.3. Definition of enrollment

After participants signed informed consent, they were randomized before the endoscopic ultrasonography. The randomization time was the enrollment time, and was recorded in CRF.

4. Endpoints

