6.2.3 Subject identification number

Patients were numbered after signing informed consent.

The subject number begins with EA as a fixed number and is numbered starting from 0001 at the time of signing the informed consent. For example, the first patient who signed the informed consent was EA0001, and the second one was EA0002.

Once the subject identification number is assigned, the number is not reusable.

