6.4.1 Pre-Procedure

In any time during the study period, even before EUS, participants could withdraw their informed consent whenever necessary. Researchers can withdraw participants before surgery according to safety considerations in the inclusion and exclusion criteria.

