6.5.2 Blinding Implementation and Protection

Subjects and evaluators are blinded according to the protocol.

Randomization results will be kept confidential to the subjects in general. Randomization results are not reflected in inpatient history and other subject access documents. During and after the examination, study personnel should take care not to talk to the subject about the results of the randomization to avoid unnecessary unblinding.

The assessors are blinded, and the data analysis team and pathologists could not obtain the randomization results from the medical history data.

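### Section 6.5.1 fixes one block size of 4 in a single-centre trial whose operators see the arm, and does not restrict sight of past allocations: a limited, cheaply removed risk that allocations are foreseen shortly before randomisation

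*Combined protocol and SAP*

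**What the plan says.** Section 6.5.1 describes electronic randomisation: "the random contents are implemented in an electronic system block-randomized manner ($n = 4$; experimental group/control group = 1"). I read n = 4 as the block size, which is the natural reading although the words block size do not appear. No other size, random variation or stratification is stated, and section 5.2 makes the trial single-centre, so there is one allocation stream. Section 6.5.1 also appears to have the researchers carry out the randomisation, and says that "the generated random results were stored in the research center". It does not say who may read them.

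The synopsis (Study Process) has the operator work with or without the AI prompt, so the operator knows the arm once the examination starts. Section 6.5.2 says "Subjects and evaluators are blinded according to the protocol"; operators and enrolling staff are not listed.

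Three provisions leave room for judgement about who enters or stays:

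- Section 3.2, item 8, excludes a patient when "Researchers believe that the patient is not suitable to participate in the trial".
- Section 3 allows a consented patient to be excluded on endoscopists' "professional advices/medical reasons (only under very limited conditions to avoid researcher bias").
- Section 6.4.1 says "Researchers can withdraw participants before surgery according to safety considerations in the inclusion and exclusion criteria".

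On timing, the table in section 1.1 puts the inclusion/exclusion check in screening (day -30 to -1) and randomisation on day 0. Section 3.3 says "The randomization time was the enrollment time". Section 6.2.3 says "Patients were numbered after signing informed consent", so subject numbers do not mark position within a block.

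**The concern.** With a known block size of 4 at 1:1, anyone following the sequence can deduce the last allocation of each block, and sometimes the third. An electronic system may hide the next allocation, but it cannot stop deduction from past ones. If a person who can do this also judges suitability shortly before randomisation, removals could differ by expected arm. A patient removed at that stage has no arm, so neither the FAS nor the PP comparison of section 8.5 would reveal the selection.

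The plan recognises the general hazard. Section 6.5.3 warns that disclosing one subject's result can expose those of others, and section 3 limits endoscopist-advised exclusions for the sake of avoiding researcher bias. It does not connect either safeguard to the block size or to access to past allocations.

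**Working it through.** **Inputs.** Block size 4 and ratio 1:1 (section 6.5.1); one centre (section 5.2); 285 patients (section 8.4). The share q of earlier allocations that a staff member sees, and the number g of other patients randomised between the decision and the allocation, are not in the documents. I treat both as assumptions and vary them.

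**The plan's own figure.** The plan gives no figure for predictability. Its total of 285 reproduces with the unpooled two-proportion formula: (1.960 + 0.842)² × (0.08 × 0.92 + 0.20 × 0.80) / 0.12² = 127.3, so 128 per arm and 256 in total; 256 / 0.90 = 284.4, rounded up to 285. It is used below only as a multiplier.

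**Upper bound (q = 1, g = 0, block boundaries known).** A block has 6 equally likely sequences. In 2 (AABB, BBAA) the last two positions are determined; in the other 4 only the last is.

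- Certain per block: (2 × 2 + 4 × 1) / 6 = 4/3, and (4/3) / 4 = 33.3%.
- In 285 patients (71 full blocks plus 1): 71 × 4/3 = 94.7, about 95. In simulation the 2.5 to 97.5 percentile range is 87 to 103.
- Best guess by position: 1/2, 2/3, 2/3, 1. Mean = 2.833 / 4 = 70.8%.

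**Boundaries not known at the start.** An observer who sees every allocation but does not know where blocks begin identifies the position after a median of 13 allocations (simulation). The certain share is then 31.8% and the best guess 70.7%. Not knowing the boundaries is little protection against a full tracker.

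**Only a share q seen (g = 0, boundaries known).** Position 3 is certain with probability q²/3 (both predecessors seen and equal). Position 4 is certain with probability q² (both members of the used-up arm seen). Certain share = (q²/3 + q²) / 4 = q²/3. The columns for random sizes come from simulation, with an observer who knows the set of sizes.

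| q | Fixed 4: certain | Fixed 4: best guess | Random 4/6/8: certain | Random 4/6/8: best guess |
|---|---|---|---|---|
| 1 | 33.3% | 70.8% | 2.3% | 68.0% |
| 0.75 | 18.8% | 64.6% | 0.3% | 61.3% |
| 0.5 | 8.3% | 59.9% | under 0.1% | 57.8% |
| 0.25 | 2.1% | 55.4% | 0% | 54.6% |

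**Gap between decision and allocation (fixed 4, q = 1, boundaries known).** With g = 1, position 4 is certain only if positions 1 and 2 were equal (probability 1/3), so the certain share is (1/3) / 4 = 8.3%. The best guess is (1/2 + 1/2 + 2/3 + 2/3) / 4 = 58.3%. With g = 2, only position 4 carries any information: (3 × 1/2 + 2/3) / 4 = 54.2%.

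| Other patients randomised in between | Certain | Best guess |
|---|---|---|
| 0 | 33.3% | 70.8% |
| 1 | 8.3% | 58.3% |
| 2 | 0% | 54.2% |
| 3 or more | 0% | 50% |

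**What each part of the fix achieves.** Varying the size removes nearly all certainty but lowers the best guess by only about 1 to 3 points at any given q. Reducing q is what moves the best guess toward 50%.

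**The case against.** The strongest objection is timing. One third needs a decision made immediately before that patient's allocation, by someone who has seen everything so far. The section 1.1 table puts the eligibility check in screening. A suitability judgement made then, with three or more patients randomised before that patient's turn, gains nothing from the block structure. This stands, and it is why one third is stated only as an upper bound.

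The overlap of roles is also undocumented. Section 6.2.1 gives eligibility to the investigator or a trained designee, and the synopsis gives the procedure to the operating physician. Nothing says that these are the same people, that one operator sees all cases, or that eligibility staff can read the stored results. Storage at the centre describes a location, not access rights. This stands too.

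The late routes are narrow: section 3 restricts endoscopist-advised exclusions and section 6.4.1 ties withdrawals to safety. The documents do not say whether either kind of removal comes before or after randomisation, and this point concerns only those before it.

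Removals also leave a trail: logged screening reasons (6.2.2), numbers never reused (6.2.3), no replacement (6.4.3) and randomisation times to the minute (6.5.1). That helps later tracing but makes the next allocation no less predictable.

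A reader might infer that about 95 of the 285 allocations will be foreseen, or that selection bias is present. The documents support neither. The 95 counts allocations that a full tracker could deduce with no gap, not patients about whom anyone has a decision left to make.

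**Conclusion.** The point holds in a limited form. Section 6.5.1 fixes and prints a single small block size for one unblinded allocation stream, and sets no limit on who sees past allocations. The largest possible exposure is one third of allocations known with certainty and a best guess of 70.8%, assuming full tracking and no gap before allocation. Partial sight or a short gap reduces it quickly: the certain share is 8.3% with half of allocations seen, also 8.3% with one intervening patient, and zero with two or more.

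What remains exposed is the set of discretionary removals made shortly before randomisation. The documents give neither its size nor the overlap between eligibility staff and those who see allocations. No bias is shown and no size of bias is claimed. This is a low-priority improvement worth making because it costs so little; the sample size of 285 is unaffected.

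**What to change.** 1. Set the electronic system to randomly varying block sizes, for example 4, 6 and 8, and keep the sizes in a restricted file rather than in the protocol.
2. Reword section 6.5.1 along these lines: *Allocation is 1:1 by computer-generated permuted blocks of varying size. The electronic system releases each allocation only after eligibility has been confirmed and locked. Staff who judge eligibility have no access to the sequence or to the list of past allocations.*
3. Report the number of consented patients removed before randomisation, with the reasons already logged under section 6.2.2.

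Items 1 and 2 belong together: under full tracking, varying the size cuts certain deductions to about 2% but leaves the best guess at about 68%. Even with both, operators will still see the arms of the patients they examine, so this reduces the risk and does not abolish it.

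The cost is one block-size setting, one access-rights setting, one reworded paragraph, one restricted file and one reported count. At exactly 285 patients the final imbalance between arms becomes at most 3 instead of 1 (for other totals, at most 4 instead of 2), which is negligible.

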6.5.2 Blinding Implementation and Protection

Subjects and evaluators are blinded according to the protocol.

Randomization results will be kept confidential to the subjects in general. Randomization results are not reflected in inpatient history and other subject access documents. During and after the examination, study personnel should take care not to talk to the subject about the results of the randomization to avoid unnecessary unblinding.

The assessors are blinded, and the data analysis team and pathologists could not obtain the randomization results from the medical history data.

6.5.3 Unblinding

Uncovering or breaking the blindness means displaying the randomized results to the subjects or evaluators. Researchers should protect the blind method as far as possible. Uncovering the randomized results of a single subject may lead to the leakage of the randomized results of other subjects. Any leakage of the randomized results will have a significant impact on statistical analysis. In general, it is prudent to deal with the disclosure of blind law. In the following cases, it is possible to consider the disclosure of blind law:

- 1) endangering the safety of subjects: For example, in some serious adverse events, subjects need to know the randomized results to inform other physicians to take appropriate emergency treatment.
- 2) Threatening the safety of the assessor: When the assessor is facing potential safety hazards, he needs to know the randomization results.
- 3) Compliance: For reasons of partial compliance, in certain circumstances, if the research instruments and cases involved in unexpected adverse events are needed, the results of randomization should be made public to the relevant departments or the public.
- 5) Other management reasons.

6.6 Concomitant therapy and medication

The concomitant treatment and concomitant medication were recorded from the time the subject signed the informed consent to the time the study was completed. Concomitant treatment and concomitant medication should be recorded in the CRF, or a clear copy of the form available from the research center should be kept in the CRF as research data to identify other factors affecting the end of the study. When recording the concomitant treatment and concomitant medication, the indications and the starting and ending time of use should be clearly defined, and the corresponding types of adverse events should be indicated for the treatment measures to cope with adverse events. When using a copy of the study center form, the investigator should sign the copy and indicate the date of review to confirm that the document is a study document.

7. Basis of study protocol and risk/benefit analysis

EndoAngel is used to provide assistant to monitor the operation of endoscopists, which will not provide diagnosis. Doctors make their own diagnosis on the basis of EndoAngel's results. The security of the software and the improvement of endoscopic physician's diagnosis and treatment level have also been confirmed in the previous feasibility study. And the patients in this study carry out the diagnosis and treatment according to the conventional treatment measures, which are formulated in accordance with the standard medical treatment procedures and do not increase the risk of the subjects.

7.1. Selection of endpoints

1、The primary outcome of the study are the Missed scanning rate of adjacent important anatomical structures in pancreatic endoscopic ultrasonography.

The secondary outcomes of this study were: 1.Pancreatic lesions detection rate; 2.Cholangiopancreatic duct lesions detection rate; 3.The average number of scanning in the pancreatic standard station of endoscopic ultrasonography; 4.Detection rate of lesions in different pancreatic standard stations of endoscopic ultrasonography; 5.Missed scanning rate of adjacent vital anatomical structures in different pancreatic standard stations of endoscopic ultrasonography; 6.Mean scanning time in different pancreatic standard stations of endoscopic ultrasonography.

Adverse events in safety indicators shall be judged in accordance with relevant regulations, and serious adverse events shall be recorded and reported in accordance with regulations.

Other evaluations are detailed in the Case Report Form (CRF).

7.2. Definition of participants

Patients were included according to the indications and contraindications described in the use

plan. Because of practical reasons (such as younger patients, participation in a number of clinical studies, alcohol/drug dependence patients, and other factors that may affect the completion and/or reliability of gastroscopy) and ethical reasons (whether informed consent can be completed, etc.), the entry and discharge criteria have been reduced.

7.3. Adverse events

The relevant definitions of adverse events are as follows:

Adverse Events (AE): Any adverse medical event, unexpected disease or injury, or adverse clinical manifestations (including abnormal laboratory findings) that occur in a subject, user or other person, whether or not associated with medical devices.

Serious Adverse Events (SAE): Adverse Events with the following information:

- causing death.
- leading to severe deterioration of the health of the subjects, including
- leading to life-threatening diseases or injuries,
- Causing impairment of body structure or function.
- Need hospitalization or extended hospitalization
- lead to hospitalization and preventive medical or surgical intervention
- Permanent damage to body structure or function
- Fetal distress, fetal death or congenital abnormalities or congenital defects.

Note: Hospitalization for existing conditions, or surgery required in the program, without serious deterioration of health status, is not considered a serious adverse event. Purposeful hospitalization, such as economic or reimbursement reasons, is not considered a serious adverse event.

Unexpected adverse device response (UADE): refers to adverse events related to medical devices that were not previously identified in the current version of the risk analysis report in terms of nature, severity or incidence. The definition includes any event caused by insufficient or inadequate description of the use or deployment of the device. This definition includes any event caused by a user's error.

7.4. Expected and trial-related adverse events

Previous studies have shown that the expected adverse events are basically the same as the complications of conventional endoscopic diagnosis and treatment.

The instrument used in this experiment is a medical software which is not in contact with human body. There is no difference between the experimental operation and the routine operation. The intervention measures (such as randomized process) in the experiment may slightly increase

the incidents of diagnosis and treatment.

7.5. Risk minimization

In this study, when there are bugs in the software, doctors can still operate under their own judgment without affecting conventional diagnostic and treatment measures, greatly reducing the risk of the test.

7.6. Related benefits

Subjects will be randomly assigned to an experimental group or a control group. And experimental subjects may increase the detection of pancreatic lesions and other lesions.

7.7. Overall feasibility analysis

EndoAngel is an independent system including both software and computer hardware, which can monitor image data 24 hours a day. The system is not invasive. The overall operability is strong.

8. Statistical Analysis

8.1. Statistical Analysis Plan

Data management and statistical analysis were implemented by Renmin Hospital Wuhan University.

8.2. Methods

Continuous variables should be described by number of subjects, mean, standard deviation, median, minimum and maximum. The classification variables are summarized by frequency and percentage.

8.3. Hypothetical test

The main assumptions are:

1. The use of EndoAngel can reduce the missed scanning rate of adjacent important anatomical structures in pancreatic endoscopic ultrasonography.
2. The use of EndoAngel can improve the the detection rate of Pancreatic lesions.

8.4. Sample Size Calculation

We mainly studied the effect of EndoAngel on the quality of EUS scanning for physicians. Therefore, data collection and analysis were conducted for the main effect. It is expected that a total of 285 subjects will be enrolled. Assuming the missed scanning rate of adjacent important anatomical structures in experimental group is 8%, the missed scanning rate of adjacent important anatomical structures in control group is 20%. Bilateral significance level 5% (alpha =5%), assurance 80% (beta =20%), shedding rate 10%, Expected to enroll 285 patients in total.

